6.4 Efficacy Analysis

6.4.1 Analysis Population

Analysis populations, treatment groupings, and datasets are detailed in Section 6.2 above.

The analysis populations, treatment groupings, and datasets for efficacy analyses will be as follows:

- Primary efficacy analyses of non-MRI endpoints will utilize the Study 109MS303 ITT Population with Combined Treatment Grouping and Combined Data;
- Primary efficacy analyses of MRI endpoints will utilize the Study 109MS303 MRI Cohort with Combined Treatment Grouping and Combined Data;
- The efficacy analysis of Study 109MS303 ARR will utilize the Study 109MS303 ITT Population with Combined Treatment Grouping and Study 109MS303 data only.

6.4.2 Analysis Methods

In general, the covariates included in the statistical models for efficacy endpoints are selected to be consistent with analysis models in other previously reported Phase 3 MS studies. In these studies, the covariates have been demonstrated to be important factors in the analyses of the efficacy endpoints. Additionally, the statistical models and the covariates for inclusion in these statistical models for the efficacy analyses for Study 109MS303 will generally be the same as the corresponding models in Studies 109MS301 and 109MS302.

Consistent with the efficacy analysis conventions in Studies 109MS301 and 109MS302, in general, for efficacy analyses of Study 109MS303, observed data after first use of alternative MS medications in the given dataset will be excluded, or subjects will be censored at the time of first starting alternative MS medication in the given dataset if they have not experienced the event of interest. The exceptions to this are:

- Select sensitivity analyses that may be performed which consider all data regardless of alternative MS medication usage; and
- Analysis of disability progression based on EDSS, where EDSS evaluations
 performed after first use of alternative MS medication has been started will be used to
 confirm tentative progression that occurred prior to first use of alternative MS
 medication.

Alternative MS medications may include but are not limited to: interferon beta-1a, glatiramer acetate (for those subjects not receiving study-assigned GA), natalizumab, interferon beta-1b, mitoxantrone, mycophenolic acid, mycophenoloate mofetil, plasmapheresis used for the indication of MS, fingolimod, methotrexate, azathioprine,

alemetuzumab, ocrelizumab, teriflunomide, siponimod, daclizumab, cladribine, peginterferon beta-1a, cyclophosphamide, and rituximab.

Region as a covariate or in the subgroup analysis is based not only on considerations of geography but also on type of health care system and access to health care in each country. The categories for regions will be identical to those used in Studies 109MS301 and 109MS302:

- Region 1: United States (including Puerto Rico);
- Region 2: Western European countries (including Austria, Belgium, France, Germany, Greece, Ireland, Italy, Netherlands, Spain, Switzerland, and United Kingdom), plus Australia, Canada, Costa Rica, New Zealand, Israel, and South Africa; and
- Region 3: Eastern European countries (including Belarus, Bosnia And Herzegovina, Bulgaria, Croatia, Czech Republic, Estonia, Latvia, Macedonia, Moldova, Poland, Romania, Serbia, Slovakia, and Ukraine), India, Guatemala, and Mexico.

The following table includes endpoints, analysis populations, baseline type with a short summary of statistical methods for the major efficacy analyses. Sections below include more details about these analyses.

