6.3.6 Study Drug Compliance and Time on Study

Study drug compliance in Study 109MS303 will be summarized. The number of capsules not taken since the previous visit (out of those capsules the subject was expected to take) is collected on the study drug accountability CRF page. Using this information, percentage compliance will also be calculated as follows:

Total number of capsules not taken is calculated as the sum of all individual values of the number of capsules not taken since the previous visit for a subject, as defined above.

Total number of capsules assigned is calculated based on the number of days on study medication for a subject. The calculation of number of days on study medication is detailed below.

Percentage compliance is then calculated as: [(Total number of capsules assigned) – (Total number of capsules not taken)] / (Total number of capsules assigned) * 100.

Percentage compliance will be calculated up to the date of last dose in Study 109MS303.

In addition, the total time on study medication will be summarized as a continuous variable and categorized into intervals. Days on study medication is calculated as the number of days from date of first dose to date of last dose. Additionally, the total number of subject-years of exposure to study medication will be presented. Time on study medication will be summarized for Study 109MS303 only and for Combined Data, utilizing the Study 109MS303 ITT and Safety populations.

Time on study parameters, including overall time on study and time on study prior to first use of alternative MS medication, will be summarized as a continuous variable and categorized into intervals. Total number of subject-years for time on study, both overall and prior to first use of alternative MS medication, will also be presented with respect to the dataset analyzed. The last known date on study will be taken as the last visit/evaluation date from relevant data for a subject. Summaries will be performed for Study 109MS303 only and for Combined Data, utilizing the Study 109MS303 ITT population. Additionally, overall time on study in Study 109MS303 will be summarized utilizing the Study 109MS303 Safety population.

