6.3.7 Concomitant Medications and Non-drug Therapies

Concomitant medications are defined as any medications take on or after the day of first dose of study treatment and on or before the day of last does of study treatment in the given dataset. This includes medications started prior to the first dose of study treatment in the given dataset and continued while on study or started after the first dose of study treatment. A windowing rule of +180 days may be applied to these subjects who have completed the study without lymphocyte follow-up. The WHO drug dictionary will be used for coding concomitant medications.

Concomitant medications will be summarized using the Study 109MS303 ITT Population and Study 109MS303 data only. The number and percent of subjects taking concomitant medications will be summarized. The most frequently taken concomitant medications, defined as those taken by at least 10% of subjects in any treatment group, will also be presented.

Additionally, summaries of first alternative MS medication used may be performed using the following analysis populations, treatment groupings, and datasets:

- Study 109MS303 ITT Population and Combined Data; and
- Study 109MS303 ITT Population and Study 109MS303 data only.

The number and percent of subjects in Study 109MS303 who previously took alternative MS medications in Studies 109MS301 or 109MS302 will also be summarized.

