6.4.2.1 Table of summary of major efficacy analyses for the 109MS303 ITT population

Endpoint	Population	Data	Treatment Grouping	Baseline	Statistical Methods
Annualized relapse rate	109MS303 ITT population	Combined Data	Combined Treatment Grouping	109MS301/109MS302 Baseline	Unadjusted and adjusted ARR. Adjusted ARR will be estimated from the negative binomial model, adjusted for baseline EDSS (<=2.0 vs >2.0), baseline age (<40 vs >=40), region and number of relapses in the 1 year prior to 301/302 study entry. If convergence criterion is not met, then Poisson regression will be used.
		109MS303 Data	Combined Treatment Grouping	109MS301/109MS302 Baseline	Unadjusted and adjusted ARR. Adjusted ARR will be estimated from the negative binomial model, adjusted for baseline EDSS (<=2.0 vs >2.0), baseline age (<40 vs >=40), region and number of relapses in the 1 year prior to 301/302 study entry. If convergence criterion is not met, then Poisson regression will be used.
Annualized relapse rate by yearly interval	109MS303 ITT population	Combined Data	Combined Treatment Grouping	109MS301/109MS302 Baseline	Unadjusted and adjusted ARR. Adjusted ARR will be estimated from the negative binomial model, adjusted for baseline EDSS (<=2.0 vs >2.0), baseline age (<40 vs >=40), region and number of relapses in the 1 year prior to 301/302 study entry. If convergence criterion is not met, then Poisson regression will be used.
		109MS303 Data	Combined Treatment Grouping	109MS301/109MS302 Baseline	Unadjusted and adjusted ARR. Adjusted ARR will be estimated from the negative binomial model, adjusted for baseline EDSS (<=2.0 vs >2.0), baseline age (<40 vs >=40), region and number of relapses in the 1 year prior to 301/302 study entry. If convergence criterion is not met, then Poisson regression will be used.

Endpoint	Population	Data	Treatment Grouping	Baseline	Statistical Methods
Proportion of subjects	109MS303	Combined Data	Combined Treatment	109MS301/109MS302	Kaplan-Meier curve of time to first relapse will be
who relapsed at selected	ITT population		Grouping	Baseline	used to estimate the proportion at selected time
time points					points.
Proportion of subjects	109MS303	Combined Data	Combined Treatment	109MS301/109MS302	Kaplan Meier analysis of time to the 6-month
with 6-month sustained	ITT population		Grouping	Baseline	sustained disability progression will be used to
disability progression					estimate the proportion at selected time points.

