Annualized relapse rate (ARR) will be summarized using the following analysis populations, treatment grouping, and datasets:

- Studies 109MS301/302/303 ARR, overall and over time, using the Study 303 ITT Population with Combined Treatment Grouping and Combined Data; and
- Study 109MS303 ARR using the Study 303 ITT Population with Combined Treatment Grouping and Study 109MS303 data only.

The number of subjects with a given number of relapses (categories of 0, 1, 2, 3, and 4 or more relapses), total number of relapses, and total number of subject-years of follow-up will be summarized by treatment group. The unadjusted ARR will be calculated for each treatment group as the total number of relapses divided by the total number of subject-years

of follow-up. Relapses and follow-up time that occur after first use of alternative MS medications are excluded from the calculations.

The adjusted ARR and associated 95% confidence interval will be calculated for each treatment group by using a negative binomial regression model for unadjusted ARR, adjusting for baseline EDSS score (≤2.0 vs. >2.0), baseline age (<40 vs. ≥40 years old), region, and baseline relapse rate (i.e., the number of relapses in the year prior to the date of first dose in the previous study) as covariates. The baseline definition for these covariates will be based on Previous Study Baseline.

The logarithmic transformation of the time on the study will be included in the model as the "offset" parameter. If the data are underdispersed, or if the negative binomial regression model does not converge, a Poisson regression model with the same covariates will be used instead of the negative binomial regression model. Dispersion will be evaluated from the Pearson Chi-Square statistic. If the ratio of the Pearson Chi-Square statistic to the degrees of freedom is ≤ 1 which indicates no overdispersion, then a Poisson regression model with adjustment for underdispersion will be used.

In addition, the subject relapse rate will be calculated as the number of relapses for an individual subject divided by follow-up time in years for that subject excluding follow-up time after first use of alternative MS medication. Subject relapse rate will be summarized descriptively by treatment group.

ARR analyses over time will be presented by various time intervals in order to elucidate onset and maintenance of effect over time. For example, time intervals one year in length may be considered.

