For ARR analyses, data following first use of alternative MS medications in the given dataset used for analysis will be excluded. If a subject did not experience a relapse prior to first starting an alternative MS medication, the subject's follow-up time will be censored at the time the first alternative MS medication is started. Likewise, if a subject did not experience a relapse prior to study withdrawal, the subject's follow-up time will be censored on the last date followed. The start date for calculation of ARR will be date of first dose, and if date of first dose is incomplete, date of randomization or enrollment will be used.

Proportion of Subjects Who Relapsed

The proportion of subjects who relapsed will be summarized using the following analysis populations, treatment grouping, and datasets:

• Studies 109MS301/302/303 proportion relapsed using Study 303 ITT Population with Combined Treatment Grouping and Combined Data.

The proportion of subjects relapsed can be estimated as the probability of relapses from the Kaplan-Meier curve of the time to the first relapse (i.e., Kaplan-Meier product-limit estimator). If there are no early withdrawals, the Kaplan-Meier estimate of the proportion of subjects relapsed is the same as the observed proportion of subjects relapsed. If there are early withdrawals, the Kaplan-Meier estimate has the advantage of taking into account the length of follow-up for the early withdrawals, without making any assumptions about whether those subjects relapsed or not.

Proportion relapsed analyses over time will be presented based on Kaplan-Meier curves. The estimated proportion of subjects relapsed at key timepoints from the Kaplan-Meier curves will be presented.

For proportion relapsed analyses, data following first use of alternative MS medications will be excluded. If a subject did not experience a relapse prior to first starting an alternative MS medication, the subject will be censored at the time the first alternative MS medication is started. Likewise, if a subject did not experience a relapse prior to study withdrawal, the subject will be censored on the last date followed. The start date for calculation of time to relapse will be date of first dose, and if date of first dose is incomplete, date of randomization will be used.

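### The Combined Data ARR drops all extension data of subjects who switched MS therapy in the parent study, and no rule keeps an entry gap of up to 6 months out of its follow-up time

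*SAP*

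**What the plan says.** **Dataset.** SAP 6.2.3 defines Combined Data as data from all three studies. SAP 6.4.1 makes it the dataset for the primary non-MRI efficacy analyses. SAP 6.4.3 lists "Studies 109MS301/302/303 ARR, overall and over time, using the Study 303 ITT Population with Combined Treatment Grouping and Combined Data".

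**Exclusion.** SAP 6.4.2 sets the general rule that "observed data after first use of alternative MS medications in the given dataset will be excluded, or subjects will be censored at the time of" their first such use. SAP 6.4.3 repeats the rule for relapse rates: "For ARR analyses, data following first use of alternative MS medications in the given dataset used for analysis will be excluded". The one all-data alternative, in 6.4.2, is a sensitivity analysis that may be performed. No endpoint or dataset is named for it.

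**Who entered.** Protocol 8.1 and SAP 2.1 admit subjects who took an approved alternative therapy in the parent study and completed the modified visit schedule. All received BG00012 in 109MS303.

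**Related outputs.** The table in SAP 6.4.2.1 has a row "Annualized relapse rate by yearly interval" for both Combined Data and 109MS303 data. SAP 6.3.7 adds: "The number and percent of subjects in Study 109MS303 who previously took alternative MS medications in Studies 109MS301 or 109MS302 will also be summarized". SAP 6.3.6 adds: "Total number of subject-years for time on study, both overall and prior to first use of alternative MS medication, will also be presented".

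**Follow-up time.** In SAP 6.4.3, time runs from first dose to the last date followed, with log time on study as the offset. The only time taken out is that after alternative MS medication. SAP 2.2 allows randomization within 6 months of parent Visit 24 (Week 96) when the two visits cannot be combined.

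**The concern.** SAP 6.4.3 states the purpose of the yearly display: "ARR analyses over time will be presented by various time intervals in order to elucidate onset and maintenance of effect over time". A reader will compare parent years with extension years. If some subjects are present early and absent later for reasons linked to their disease, part of any change in ARR is a change in who is counted.

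Such a link is plausible for one group. Protocol 8.2 (Exclusions 2 and 3) admits subjects who stopped BG00012 only if they stopped for relapse or disability progression and followed the modified schedule. The documents give no comparable information for switchers from placebo or glatiramer acetate.

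The excluded extension data are also largely on-treatment data. These subjects received BG00012 in 109MS303, and Protocol 11.6 generally bars other MS therapies.

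The entry gap is a separate matter. Neither study schedules a relapse assessment between the end of parent follow-up and 109MS303 entry. Counting that time as follow-up lowers the ARR of the interval that holds it.

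**Working it through.** The documents give no ARR, switcher count or gap count, so there is no stated figure to reproduce. The inputs are the 96 parent weeks (Protocol 5.2), the 384 extension weeks (SAP 2.2) and the 6-month entry window, taken as 26 weeks. Anything else is marked as an assumption.

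**1. What one switcher loses**

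- Extension share of scheduled time: 384 / (96 + 384) = 80%, all dropped.
- With the parent time after the switch added, the dropped share is (480 − switch week) / 480: 95%, 90% and 85% for a switch at Week 24, 48 and 72.
- If switch dates were uniform over Weeks 0–96 (assumption), the share of switchers' time still counted would be 75% in parent year 1, 25% in parent year 2 and 0% in the extension. The loss builds up over the parent years; there is no sudden step at 109MS303 entry.

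**2. Possible selection effect (illustration only)**

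Let s be the switchers' share of all extension time and r their extension relapse rate relative to other subjects. Relative to all data:

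extension-year error = 1 / (1 + s(r − 1)) − 1

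| s | r = 0.5 | r = 1 | r = 2 | r = 3 |
|---|---|---|---|---|
| 2% | +1.0% | 0 | −2.0% | −3.8% |
| 5% | +2.6% | 0 | −4.8% | −9.1% |
| 10% | +5.3% | 0 | −9.1% | −16.7% |

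Neither s nor r is in the documents. The range includes zero and both signs.

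**3. Entry gap**

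A full gap runs from Week 96 to Week 122. The group figures assume that no relapse in the gap is recorded, that subjects otherwise have full follow-up, and that a share g of them has the full gap.

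- Year 2 (Weeks 52–104) holds 8 weeks of the gap: 8/52 = 15.4% of that subject's year.
- Year 3 (Weeks 104–156) holds 18 weeks: 18/52 = 34.6%.
- Group year-3 error = −g × 18/52: −1.7% at g = 5%, −6.9% at g = 20%.
- Group year-2 error = −g × 8/52: −0.8% to −3.1%.
- Overall error = 480 / (480 + 26g) − 1: −0.27% to −1.07%.
- With 48-week study years, the whole gap falls in Weeks 96–144: 26/48 = 54.2% for one subject, and −2.7% to −10.8% for the group.
- If parent follow-up ran to Week 100 (the end visit in Protocol 5.2 for subjects not choosing to enroll), the gap is 22 weeks: 4 in year 2 and the same 18 in year 3.

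**4. Does the 109MS303-only yearly ARR fill the hole?**

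Only in part. It has no parent years. Its year 1 starts at first 109MS303 dose: Week 96 without a gap or Week 122 with a full one, against Week 104 for Combined year 3. The two series are therefore offset by −8 to +18 weeks.

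**The case against.** The strongest reply is that these data are analysed elsewhere. The table in SAP 6.4.2.1 commits to 109MS303-only ARR, overall and yearly, in the same population and treatment grouping. Because the exclusion works within the given dataset, a parent-study switch should not remove anything there. This largely stands. A reader might infer that switchers' extension relapses are never reported; the documents do not support that.

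The retention is implied rather than stated. SAP 6.3.7 says of concomitant medications: "This includes medications started prior to the first dose of study treatment in the given dataset and continued while on study". But that defines a medication summary, and Protocol 11.6 makes carry-over past the first 109MS303 dose an edge case. What remains is that no committed analysis follows one set of subjects from parent to extension years.

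A reader might also infer that the rule makes BG00012 look better. The documents do not show this: the size and sign are unknown, and the restriction in Protocol 8.2 covers BG00012 discontinuers only.

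The rule is also a declared convention from the parent studies, and it suits groups labelled by the same BG00012 dose in both studies. That is a good reason to keep it as the main analysis.

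On the gap, the SAP nowhere says that the interval counts; the point rests on the absence of a removal rule. Nor do the documents say that no relapse could be recorded in it, only that no assessment is scheduled. A combined visit is the default, and the 15%, 35% and 54% figures describe one subject with the longest gap, not a group.

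**Conclusion.** The point holds in a limited form. On the plain wording, the Combined Data ARR removes every extension relapse and all extension time of parent-study switchers, so its parent and extension years rest on different subjects. Selection is plausible for BG00012 discontinuers, but its size and direction cannot be determined from the documents.

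The gap effect, if the time rule is read literally, can only lower the affected ARR. At the assumed 5–20% of subjects with the full gap, it is about 1.7–6.9% in year 3 (52-week years) and about 0.3–1.1% overall. It therefore matters mainly for the yearly display.

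Efficacy is a secondary objective, and SAP 6.1 makes the analyses generally descriptive with exploratory testing. The change is worth making because it is cheap and the yearly display is meant to show maintenance of effect. It does not undermine the study's primary safety objective.

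**What to change.** Keep the current exclusion rule for the main analysis and add two statements to SAP 6.4.3:

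1. Commit to the all-data Combined ARR, overall and yearly, as a sensitivity analysis, to be read beside the 109MS303-only yearly ARR in the table of SAP 6.4.2.1. It keeps switchers in every year. In the extension years it should differ from the main analysis mainly through them, because subjects who start restricted medication in 109MS303 are generally withdrawn (Protocol 11.6, SAP 2.2), apart from those kept for lymphocyte follow-up.
2. In every Combined Data ARR, leave the interval between the end of parent-study follow-up and the first 109MS303 dose out of follow-up time and the offset.

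The cost is SAP wording, one extra derivation and one extra table, with no new data. The downside is that the all-data version includes effects of the intervening therapy; showing it beside the main analysis makes that visible.

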6.4.2.1 Table of summary of major efficacy analyses for the 109MS303 ITT population

Endpoint	Population	Data	Treatment Grouping	Baseline	Statistical Methods
Annualized relapse rate	109MS303 ITT population	Combined Data	Combined Treatment Grouping	109MS301/109MS302 Baseline	Unadjusted and adjusted ARR. Adjusted ARR will be estimated from the negative binomial model, adjusted for baseline EDSS (<=2.0 vs >2.0), baseline age (<40 vs >=40), region and number of relapses in the 1 year prior to 301/302 study entry. If convergence criterion is not met, then Poisson regression will be used.
		109MS303 Data	Combined Treatment Grouping	109MS301/109MS302 Baseline	Unadjusted and adjusted ARR. Adjusted ARR will be estimated from the negative binomial model, adjusted for baseline EDSS (<=2.0 vs >2.0), baseline age (<40 vs >=40), region and number of relapses in the 1 year prior to 301/302 study entry. If convergence criterion is not met, then Poisson regression will be used.
Annualized relapse rate by yearly interval	109MS303 ITT population	Combined Data	Combined Treatment Grouping	109MS301/109MS302 Baseline	Unadjusted and adjusted ARR. Adjusted ARR will be estimated from the negative binomial model, adjusted for baseline EDSS (<=2.0 vs >2.0), baseline age (<40 vs >=40), region and number of relapses in the 1 year prior to 301/302 study entry. If convergence criterion is not met, then Poisson regression will be used.
		109MS303 Data	Combined Treatment Grouping	109MS301/109MS302 Baseline	Unadjusted and adjusted ARR. Adjusted ARR will be estimated from the negative binomial model, adjusted for baseline EDSS (<=2.0 vs >2.0), baseline age (<40 vs >=40), region and number of relapses in the 1 year prior to 301/302 study entry. If convergence criterion is not met, then Poisson regression will be used.

Endpoint	Population	Data	Treatment Grouping	Baseline	Statistical Methods
Proportion of subjects	109MS303	Combined Data	Combined Treatment	109MS301/109MS302	Kaplan-Meier curve of time to first relapse will be
who relapsed at selected	ITT population		Grouping	Baseline	used to estimate the proportion at selected time
time points					points.
Proportion of subjects	109MS303	Combined Data	Combined Treatment	109MS301/109MS302	Kaplan Meier analysis of time to the 6-month
with 6-month sustained	ITT population		Grouping	Baseline	sustained disability progression will be used to
disability progression					estimate the proportion at selected time points.
measured by EDSS at		109MS303	Combined Treatment	109MS303 Baseline	Kaplan Meier analysis of time to the 6-month
selected time points		Data	Grouping		sustained disability progression will be used to
					estimate the proportion at selected time points.
EQ-5D: EQ5D VAS,	109MS303	Combined Data	Combined Treatment	109MS301/109MS302	Descriptive statistics by combined treatment group
EQ-5D index score and	ITT population		Grouping	Baseline	and by study visit.
EQ-5D individual					
questions					
SF-36 scores	109MS303	Combined Data	Combined Treatment	109MS301/109MS302	Descriptive statistics by combined treatment group
	ITT population		Grouping	Baseline	and by study visit.
Visual function test	109MS303	Combined Data	Combined Treatment	109MS301/109MS302	Descriptive statistics by combined treatment group
	ITT population		Grouping	Baseline	and by study visit.
MRI endpoints	109MS303	Combined Data	Combined Treatment	109MS301/109MS302	Descriptive statistics by combined treatment group
	MRI Cohort		Grouping	Baseline	and by study visit.
					For the total number of new or newly enlarging T2
					lesions, the total number of new T1 lesions, and the
					total number of Gd-enhancing lesions: negative
					binomial models may be used, adjusted for baseline
					characteristics in previous studies.

